### 5.2 Secondary study objectives

The secondary study objectives will set pool use and waterbirth in the context of NHS care. The study will describe:

- The overall proportion and characteristics of women who use a pool for labour or birth, compared to those who do not use a pool.
- 2. The characteristics of, and outcomes for, women with identified risk factors at labour onset, who use a pool during labour.
- 3. The characteristics of, and outcomes for, women who develop labour complications who use a pool during labour.
- 4. Explore factors associated with high and low rates of pool use in individual maternity units.

### 5.3 Primary outcomes measures

The study has two primary outcomes.

The maternal primary outcome will be Obstetric Anal Sphincter Injuries (OASIS). Such trauma is important to women and the NHS as it requires more complex repair and follow-up, and is associated with short term morbidity (pain, infection, incontinence) as well as longer term morbidity; (dyspareunia, urinary and faecal incontinence, future caesarean section).

The neonatal primary outcome will be composite of 'adverse neonatal outcomes or treatment' to include: (a) any neonatal unit admission requiring respiratory support (b) antibiotic administration within 48 hours of birth (with or without culture proven infection); and (c) intrapartum stillbirth or neonatal death. Such outcomes are important as they cause distress to parents, have potential long term damage to babies and are associated with cost to the NHS. Composite neonatal outcomes combining mortality and morbidity are credible and provide more power to detect differences between groups, but the level of incidence of individual components will remain insufficient to detect differences in each outcome.

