#### 9.6 Cohort Study Statistical considerations

#### 9.6.1 Sample size

The non-inferiority of birth in water compared to birth on land on rates of OASIS will be examined by parity. The Birthplace in England study found that overall 4.6% and 1.6% of nulliparous and parous women respectively, sustained OASIS. A sample size of 15,000 nulliparous and 15,000 parous 'low risk' women (7,500 each water and land) is required to obtain 90% power, and a 95% one-sided confidence interval around a treatment difference of zero. A non-inferiority margin of 1% or less,

Page **22** of **38** 

and 0.6% or less will be taken as clinically non-significant amongst nulliparous and parous 'low risk' women respectively. Since nulliparous women birthing in water are regarded as the least prevalent of the four groups, a data collection period providing data on 7,500 would ensure adequate numbers in the other three, more prevalent groups. These data will be combined to assess the effects averaged across both strata at an increased power, with a combined required sample size of 30,000 'low risk' women. We have assumed that 25% of the 6,600 waterbirths recorded in EuroKing® in 2015 were nulliparous women (1650/annum). Allowing for staggered site set-up, five years of combined retrospective and prospective data collection would be required (January 2015 – November 2020). The exact ratio of nulliparous and parous women who give birth in water will be determined once the retrospective data are examined, but with increasing numbers of waterbirths, with 18 of the 35 EuroKing® using sites, collectively undertaking 6,037 waterbirths in 2016, we are confident the study will have sufficient power to answer this important clinical question.

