#### 9.6.5 Primary analysis

The primary analyses are based on a non-inferiority test of birth in water versus on land, comparing 1) the proportion of mothers that have OASIS, and 2)the proportion of babies with a composite outcome of 'adverse neonatal outcome or treatment'.

To test the primary hypothesis of non-inferiority between birth in water and on land, the two outcomes will be evaluated for non-inferiority using logistic regression models, in the first instance with no adjustment for covariates. Adjusting for potential confounders may result in a more precise treatment effect estimate. The potential confounders of both primary outcomes (listed in table 1) will be considered and the impact on bias through conditional associations when conditioning on these covariates will be assessed using directed acyclic graphs (DAGs). The main logistic model will incorporate these selected covariates through regression adjustment. Results will be reported as an (unadjusted) odds ratio (birth in water compared to on land), and a two-sided 90% confidence interval (CI) for the (unadjusted and adjusted) odds ratio will be calculated. Non-inferiority will be concluded if the upper limit of the 90% CI for the difference in neonatal outcome between the groups is less than 1.0% (OR<1.21). Similarly, for the mother's outcome, non-inferiority will be concluded if the upper limit of the 90% CI for the difference in the proportion of OASIS between the groups is less than 1.0% (OR<1.23) in nulliparous 'low-risk' women and less than 0.6% (OR<1.38) in parous 'low-risk' women. The data will then be combined to assess the effects averaged across both strata.

If non-inferiority is shown, then a superiority analysis will be conducted as a secondary analysis of the primary outcomes using logistic regression and will be presented as an (unadjusted and adjusted) odds ratio of outcomes in the waterbirth group compared with the birth on land group. Parameter estimates will be provided alongside 95% CI and p-value. Secondary outcomes will have non-inferiority testing as detailed above.

	Maternal	Adverse neonatal
	outcome: OASIS	composite outcome
Maternal age (years)	√	$\checkmark$
Maternal BMI	✓	
Parity	√	
Duration of labour	✓	
Gestational age at delivery (weeks)	√	$\checkmark$
Child birth weight (g)	✓	$\checkmark$
Child head circumference (cms)	√	
Maternal thyroid disease (including hypothyroidism)		$\checkmark$
Pre-labour ruptured membranes		$\checkmark$

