#### Table 1. Potential confounders for both maternal and baby outcomes

#### 9.6.6 Subgroup analysis

Maternal: A planned and powered sub group of the primary maternal outcome will be conducted to compare rates separately for primiparous and multiparous women. One previous cohort study of women using a pool during labour found that delivery of placenta in water and postpartum haemorrhage of >1,000 ml to be relatively uncommon (17% and 1% respectively). It is likely therefore that the proposed sample of 15,000 women who will give birth in a pool during the period of prospective data collection (2018 – 2020) will be underpowered to detect a difference in rates of postpartum haemorrhage between women who remain in, or leave the pool, for delivery of the placenta, but these data and outcomes will be described. The relationship between the proportion of women using a pool during labour, at individual sites and the incidence of adverse maternal and primary outcomes will be described.

TPL/003/2 v1.0

Page 25 of 38

Neonatal: A planned sub group of the primary neonatal composite outcome will also be conducted to compare rates separately for babies born to primiparous and multiparous women.

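### Table 1 gives the main OASIS model no obstetric history, and the protocol does not show that parous women with a previous severe tear are excluded

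*Protocol*

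**What the plan says.** Section 9.6.5 gives parous low-risk women their own non-inferiority conclusion on OASIS: the upper confidence limit for the difference must be "less than 0.6% (OR<1.38) in parous" women. For adjustment, "The potential confounders of both primary outcomes (listed in table 1) will be considered" with directed acyclic graphs, and the selected ones enter the main logistic model. The table is captioned "Table 1. Potential confounders for both maternal and baby outcomes". Its OASIS column has seven entries: maternal age, BMI, parity, duration of labour, gestational age, birth weight and head circumference.

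The protocol's only remark on what OASIS means for a woman later is in Section 5.3, which names "longer term morbidity; (dyspareunia, urinary and faecal incontinence, future caesarean section" as reasons why the outcome matters.

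The stated exclusions are opt-out (Synopsis) and, for the primary analysis, births before arrival or intentionally without a midwife (Section 9.6.4). Low-risk status is set by reference to NICE criteria (Sections 3 and 9.1), without listing them. The maternal analysis combines retrospective births from January 2015 with prospective births (Sections 7 and 9.3). The screening question on complicating factors at pool entry is a new item (Section 9.3). So are the maternal risk factors at pool entry and the reason for leaving the pool (Section 5.4).

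Section 15.3 adds propensity score and instrumental variable analyses as sensitivity analyses. It says that staying in the pool probably depends on age, parity and other characteristics.

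**The concern.** A previous severe tear is an earlier occurrence of the primary maternal outcome. It is fixed before labour and exists only in parous women. Parity cannot stand in for it, because women with and without such a tear can have the same parity. As Section 9.6.5 is worded, the graph step selects from Table 1 and does not add to it, so the main model has no route to this variable.

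At stake is a separate safety conclusion with a narrow margin and a low event rate. Suppose these women are in the analysis, carry a higher risk and are more common in the land group. Waterbirth then looks safer than it is. If they are more common in the water group, it looks worse. The protocol does not say which way any imbalance would run.

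**Working it through.** **Inputs from the protocol.** Section 9.6.1 states that "4.6% and 1.6% of nulliparous and parous women respectively, sustained OASIS". The parous rate is therefore p = 1.6%, with margin 0.6 points and n = 7,500 per group. The design has "90% power, and a 95% one-sided confidence interval around a treatment difference of zero".

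**The plan's own figure.** n per group = 2p(1-p) × [(1.645 + 1.282)/0.006]² = about 7,491, against 7,500 stated. The standard error at 7,500 is √(2 × 0.016 × 0.984/7,500) = 0.205 points, and power is Φ(0.6/0.205 - 1.645) = 90.0%. The odds ratio for 2.2% against 1.6% is (0.022/0.978)/(0.016/0.984) = 1.38, as stated. The sample size is sound.

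**Assumptions not in the protocol.**
- Prevalence q of a previous severe tear among parous pool users: 3% to 4.6%. The upper end borrows the nulliparous OASIS rate as a proxy.
- Relative risk RR of OASIS after a previous tear: 2 to 5.
- Gap g in that prevalence between the groups: 1 to 4 points.
- Overall parous rate held at 1.6%.

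**Formulas.** Rate without a previous tear: p0 = 0.016/(1 + q(RR - 1)). Bias in the risk difference: b = p0 × (RR - 1) × g. Chance of concluding non-inferiority: Φ((0.6 - apparent difference)/0.205 - 1.645), with differences in points.
- Land group enriched, true excess 0.6: the error is Φ(b/0.205 - 1.645).
- Water group enriched, true difference 0: the power is Φ((0.6 - b)/0.205 - 1.645).

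| q | RR | gap (points) | bias (points) | share of margin | error if land enriched | power if water enriched |
|---|---|---|---|---|---|---|
| 4.6% | 2 | 1 | 0.015 | 2.5% | 5.8% | 88.7% |
| 3% | 5 | 1 | 0.057 | 9.5% | 8.6% | 84.2% |
| 4.6% | 3 | 2 | 0.059 | 9.8% | 8.7% | 84.1% |
| 4.6% | 5 | 2 | 0.108 | 18% | 13.2% | 77.5% |
| 4.6% | 3 | 4 | 0.117 | 20% | 14.2% | 76.2% |
| 4.6% | 5 | 4 | 0.216 | 36% | 27.8% | 59.0% |
| 3% | 5 | 4 | 0.229 | 38% | 29.8% | 56.7% |

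Worked last row: p0 = 0.016/(1 + 0.03 × 4) = 1.429%, and b = 1.429% × 4 × 0.04 = 0.229 points.

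The table keeps the design standard error throughout. Recomputing it from the two apparent rates changes the last row to 27.8% error and 54.3% power, and barely changes the first. A bias of about 0.07-0.08 points, depending on the standard error used, doubles the error from 5% to 10%.

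**The case against.** The strongest objection is that the low-risk restriction is itself an eligibility filter. If its outside criteria remove women with a previous severe tear, the problem disappears. The documents do not settle this, so the objection stands as a condition. It is weaker for retrospective births, because the pool-entry screening question did not exist when those records were made. For the secondary neonatal outcomes, the protocol uses retrospective records only where the mother's risk status can be determined.

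A reader might infer from Section 5.3 that the protocol itself shows OASIS history to be a confounder. It does not. That section lists consequences in order to explain why the outcome matters. A future caesarean section takes a woman out of the pool cohort and does not by itself unbalance the women who stay against those who leave. The protocol states neither a recurrence risk nor an effect on pool exit.

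A reader might also infer that the parous conclusion is biased however exits are coded. That does not follow: the women may already be excluded, or be equally common in both groups.

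Absence from the list of new items shows little, because items that E3 already records would not appear there. The propensity score is open-ended, and the instrumental variable analysis targets unobserved selection. Both points are fair, but these are sensitivity analyses and neither names obstetric history.

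Finally, the top of the range needs strong inputs: a 4-point gap at 3% prevalence means 1% in one group against 5% in the other. That stands, which is why the range starts at a relative risk of 2 and a 1-point gap.

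**Conclusion.** The omission is real and rests on Section 9.6.5: the source list for the main OASIS model has no obstetric history, parity does not replace it, and no stated exclusion names a previous severe tear. Whether it biases the parous comparison is conditional. The women must remain after the low-risk filter, their risk must be raised, and their share must differ between the groups.

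Under the assumed ranges the bias is about 0.015-0.23 points (2.5-38% of the margin). One-sided error at the margin becomes about 6-30%, or power falls from 90% to about 57-89%, according to a direction that the documents do not fix. At a 1-point gap the bias stays below 10% of the margin; the larger figures need a wide gap and a high relative risk. This is an inexpensive improvement to a primary safety analysis. It is not evidence that the planned conclusion is wrong, and the sample size needs no change.

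**What to change.** State whether the low-risk definition removes women with a previous third- or fourth-degree tear, and whether it does so in both retrospective and prospective records. If it does, one sentence closes the point.

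If it does not, add previous third- or fourth-degree tear (yes/no) to the OASIS column of Table 1, as a candidate confounder for the parous and combined models, and to the propensity score. Take it from the obstetric history in E3 where that is held. If E3 does not hold it, collect it prospectively and run the adjusted parous analysis on prospective births as a sensitivity analysis.

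The cost is one extracted variable and one table line, plus one new E3 item if the history is not already recorded. The downside is some missing history in retrospective records.

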### 5.4 Secondary Outcomes

Secondary outcomes of parental, clinical and financial importance have been identified. Data relating to maternal or neonatal readmission to hospital within seven days of birth is already reported by community midwives and captured in EuroKing® systems at the point of discharge from midwifery care. Data relating to some primary and secondary outcomes are not currently captured in EuroKing® maternity information systems and at site opening the EuroKing® E3 systems at sites will be amended to prospectively collect these data.

Maternal secondary outcomes: Maternal Intrapartum: Shoulder dystocia and required management, management of the third stage of labour, need and reason for obstetric involvement in woman's care including sepsis; mode of birth, maternal position at birth, treatment for haemorrhage, incidence and management of perineal and other genital trauma. Maternal Postnatal: duration of postnatal stay, breast feeding initiation and continuation, higher level care, and maternal readmission to hospital within seven days of birth.

Infant secondary outcomes: Snapped umbilical cord prior to clamping, skin to skin contact at birth, timing of cord clamping, resuscitation, Apgar scores, administration and duration of intravenous antibiotics. Incidence of: lumbar puncture, culture proven infection, brachial plexus injury; treatment for jaundice; readmission to hospital within seven days of birth; therapeutic hypothermia;

TPL/003/2 v1.0

Page **15** of **38** 

neonatal unit admission and duration; cause of neonatal death; respiratory support. Where available, and where the risk status and pool usage of mothers can be determined, retrospective data will be used in addition to prospective data, to describe the occurrence of these infant outcomes.

Additional data items with accompanying background development required to fully answer the research aims will be added to E3 systems at study sites, and will include:

- Maternal risk factors at pool entry
- Maternal risk factors developing during labour
- Time of entry into pool
- Time of last leaving pool
- Reason for leaving pool if prior to birth
- Partial birth in water (breech / shoulder dystocia)
- Birth position in pool
- Conversion from planned physiological to active third stage labour management.
- Delivery of placenta in or out of water
- Treatment for haemorrhage
- Reason for obstetric involvement in woman's care
- Snapped umbilical cord prior to clamping
- Duration of antibiotics administered to neonates
- Lumbar puncture (Neonatal)
- Culture positive sepsis (Neonatal)

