### 4 Background

During labour and birth water immersion is facilitated by use of a conventional bath or more frequently a specialist birthpool. All birthpools offer sufficient depth of warm water for the woman to be immersed to above her breasts when sitting and sufficient space for ease of movement and change of position. Simple inflatable pools are available, but NHS maternity units frequently now have pools which are plumbed in, some of which are more complex with inbuilt lighting and heating. Women enter the warm water in established labour, leaving the pool either prior to birth due to clinical concerns or maternal choice, or remaining in the pool until after birth of the baby. Some mothers remain in the pool until after delivery of the placenta. For mothers the potential benefits of waterbirth are considered to be pain reduction, relaxation, reduced labour interventions and reduced perineal trauma whilst for babies, a gentle birth and transition to life. It is suggested that waterbirth may also improve longer term outcomes; mother infant bonding, increased breastfeeding and enhanced maternal postnatal mental health.

In 1992 the House of Commons Health Committee recommended that hospitals should provide women with the use of a birth pool for labour '*where this is practicable*. In the intervening years the popularity of the use of water immersion for labour and birth in the UK has increased and NICE guidance has recommended since 20071.4 that water immersion analgesia should be made available to all clinically appropriate women in labour. The Cochrane review of water immersion during labour provided evidence supportive of pool use but could not answer the question relating to the safety of waterbirth. The review included 12 trials (3243 women), eight related to just the first stage of labour: one to early versus late immersion in the first stage of labour; two to the first and second stages; and another to the second stage only. Results for the first stage of labour found a significant reduction in the epidural/spinal/paracervical analgesia/anaesthesia rate amongst women allocated to water immersion compared to no immersion (478/1254 versus 529/1245; risk ratio (RR) 0.90; 95% confidence interval (Cl) 0.82 to 0.99, six trials). There was also a reduction in duration of the first stage of labour (mean difference -32.4 minutes; 95% Cl -58.7 to -6.13). There was no evidence

TPL/003/2 v1.0

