### 5 Study objectives/endpoints and outcome measures

The primary study aim is to establish whether for 'low-risk' women who use a pool during labour, waterbirth, compared to leaving a pool prior to birth, is as safe for mothers and babies.

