### 6 Study Intervention

The health technology being assessed is giving birth in water: 'waterbirth'.

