The NNRD holds individual patient level data on all babies admitted for National Health Service neonatal care in England, Scotland and Wales from 2014 to present. To obtain detailed treatment and outcome information on any baby who required admission to a neonatal unit, following their mother's pool use in labour, the identifiers of all babies born to women who used a pool during the period of prospective data collection will be extracted and matched to any records held by the NNRD.

The primary study aim is to compare maternal and neonatal outcomes for 'low risk' women who gave birth in water (Group 1) against 'low risk' women who left the water prior to birth for reasons other than clinical need (Group 2) Figure 1.

[figure not shown]

Figure 1 Study population groups

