#### 9.6.4 Inclusion in analysis

Women, and their babies, will be included in the study if the woman used water immersion at a study site during the period of data collection. For the purposes of providing denominator data and

Page 23 of 38

to fully answer the research objectives, a minimal data set will also be obtained on women at study sites who do not use water immersion.

To capture data relating to women who use any form of water immersion during labour 'use of a pool ' during labour, will pragmatically be being any women for whom water immersion analgesia is recorded in the EuroKing E3 system.

To capture births commenced in, but completed, out of water, such as in the event of shoulder dystocia or previously unrecognised breech presentation 'waterbirth' will be defined in the study as 'A birth in which the fetus is partially or totally expelled under water'.

Data relating to women and babies recorded in EuroKing as being 'Born Before Arrival' (BBA), or recorded as intentionally born without midwifery attendance, will be excluded from primary analysis.

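### Mode of birth is sent to non-inferiority testing although the definition of waterbirth largely fixes it, so the test passes whatever the true effect; obstetric involvement carries a lesser bias towards waterbirth.

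*Protocol*

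**What the plan says.** Protocol section 5.4 places these items among the maternal intrapartum secondary outcomes: "need and reason for obstetric involvement in woman's care including sepsis; mode of birth, maternal position at birth". Section 9.6.5, after setting out the logistic models, the two-sided 90% interval and the margins for the two primary outcomes, adds: "Secondary outcomes will have non-inferiority testing as detailed above". It excepts no secondary outcome and gives no margin for any of them.

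The groups are formed as follows.

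- **Waterbirth** (section 9.6.4): "A birth in which the fetus is partially or totally expelled under water".
- **Group 2** (section 7): low-risk women "who left the water prior to birth for reasons other than clinical need (Group 2").
- **Risk status** (section 9.1) is judged at labour onset, so a complication later in labour does not by itself remove a woman from the low-risk comparison.

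The aim in section 5 is worded more loosely, as "waterbirth, compared to leaving a pool prior to birth, is as safe for mothers and babies", without the exclusion for clinical need. The Background says that women leave the pool for either clinical or personal reasons: "leaving the pool either prior to birth due to clinical concerns or maternal choice".

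**The concern.** Exposure is settled only at the moment of birth, by how and where the baby is expelled. Mode of birth is settled at the same moment by the same event. A caesarean is not an expulsion under water, and an instrumental birth can hardly be one. No section says outright that operative births count as land births, but it follows from the definition. Comparing operative birth between the groups therefore mostly recovers the rule by which the groups were made.

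Followed as written, the plan would yield a formal statement that waterbirth is non-inferior, and apparently much better, on operative birth. The study's declared outputs include information for women and NHS providers (sections 3.1 and 24). The protocol does not say that mode of birth will feature there. If it did, a reader could not tell the artefact from a finding.

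Obstetric involvement raises a related but weaker problem. Some of it arises after a woman has left the pool and before she gives birth. A woman who gave birth in water cannot have contributed events in that interval.

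**Working it through.** **1. The plan's own figures.** The protocol gives no rate or margin for mode of birth or obstetric involvement. Its sample sizes for the primary outcomes reproduce with n per group = (1.645 + 1.282)² × 2p(1 − p) / m², where p is the event rate and m the margin:

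| Outcome | p | m | n computed | n stated | OR at margin: computed (stated) |
|---|---|---|---|---|---|
| OASIS, nulliparous | 4.6% | 1.0% | 7,517 | 7,500 | 1.230 (1.23) |
| OASIS, parous | 1.6% | 0.6% | 7,491 | 7,500 | 1.383 (1.38) |
| Neonatal composite | 5% | 1.0% | 8,136 | 8,100 | 1.213 (1.21) |

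These are sound, and the point does not depend on them.

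**2. Mode of birth.** Inputs: 15,000 per group (sections 3.1 and 9.6.1); operative rate in Group 1 set to 0 (from the definition in section 9.6.4); Group 2 rate p assumed, because the protocol gives none. The upper 90% limit for water minus land is

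U = −p + 1.645 × √[p(1 − p) / 15,000].

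| Assumed p | Standard error | U |
|---|---|---|
| 1% | 0.081 points | −0.9 points |
| 2% | 0.114 points | −1.8 points |
| 5% | 0.178 points | −4.7 points |
| 10% | 0.245 points | −9.6 points |

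Against an illustrative 1-point margin, the probability of passing is 1.00 in every row. The assumed rates do not drive this. Over all values of p, U cannot exceed 1.645² / (4 × 15,000) = 0.000045, or 0.0045 percentage points. Any practical margin is met whatever the Group 2 rate.

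On the odds-ratio scale that section 9.6.5 reports, a zero cell separates the data: the maximum-likelihood log odds ratio runs to minus infinity, with or without covariates. If a few operative births were recorded in Group 1, through miscoding or births begun in water and completed out of it, the estimate would be finite but would rest on those few records.

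**3. Obstetric involvement.** Illustrative assumptions: 5% of women in each group have involvement arising at or after birth; waterbirth truly adds 2 points; a share r of Group 2 has involvement before birth, with none in Group 1; margin 1 point; 15,000 per group. Then Group 1 = 7%, Group 2 = 1 − 0.95 × (1 − r), and P(pass) = Φ[(0.01 − d) / SE − 1.645], where d is Group 1 minus Group 2.

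| r | Group 2 | d | P(pass) |
|---|---|---|---|
| 0 | 5.00% | +2.00 points | 0.00 |
| 1% | 5.95% | +1.05 points | 0.03 |
| 2% | 6.90% | +0.10 points | 0.92 |
| 5% | 9.75% | −2.75 points | 1.00 |

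The test can fail, so it is not decided by definition. But a modest share of pre-birth involvement in Group 2 is enough to hide a true 2-point excess.

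**The case against.** **Section 7 already removes women who left for clinical need.** This is the best answer to the concern, and part of it stands. Women whose complication prompted the exit are not in Group 2, so operative birth and obstetric involvement will be less common there than among all women who left. It does not rescue the mode-of-birth test. A woman who left by choice can still need an operative birth later and remains in Group 2, and step 2 shows that even a 1% rate gives an upper limit below zero. Under the looser aim in section 5 the rate would only be higher.

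**The sentence on secondary outcomes is generic.** Several items in section 5.4, such as maternal position or the reason for obstetric involvement, are categorical and have no adverse direction. The sentence cannot apply literally to all of them, and a statistical analysis plan may settle coding and margins. The synopsis list also omits mode of birth. That is fair as to how the test would be run. But section 5.4 does list the item, section 9.6.5 states the rule without exception, and no choice of coding or margin makes the operative-birth contrast informative.

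**A stronger reading is tempting: that obstetric involvement, including sepsis, also passes by definition.** The protocol does not support it. Section 5.4 does not time this outcome before birth, and involvement can follow a waterbirth, for example for haemorrhage, genital trauma or sepsis. The Background sentence on clinical exits does not describe Group 2 as section 7 defines it. What remains is a residual bias, its size unknown from the document.

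**Conclusion.** For mode of birth the point holds. The operative-birth contrast is part of the exposure classification, so a non-inferiority result is assured and says nothing about the effect of birth in water. This rests on one inference, that operative births are not expulsions under water, and on reading section 9.6.5 as written. The limits of −0.9 to −9.6 points illustrate assumed land rates of 1% to 10%; the conclusion does not depend on them.

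For obstetric involvement the point is secondary. The comparison is biased towards waterbirth by events between leaving the pool and birth, by an amount that the protocol gives no means of estimating. Whether that would change a conclusion depends on assumptions such as those in step 3.

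A reader might also infer that the primary comparisons are undermined. Nothing in this point bears on OASIS or the neonatal composite.

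**What to change.** - In sections 5.4 and 9.6.5, except mode of birth from between-group non-inferiority testing, and from any superiority step carried over to secondary outcomes. Report it descriptively for all pool users and for Group 2.
- Compare obstetric involvement between the groups only for reasons that clearly arise at or after birth, and otherwise describe it.

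The first change is wording only. The second has a limit: the reason for obstetric involvement is one of the items newly added to the maternity system (section 5.4), so it exists only for prospective births. No time of involvement is listed beside it, and a reason such as sepsis may not reveal when it arose. The comparison is feasible only where the recorded reason settles the timing. The cost is that one or two comparisons are no longer formally tested.
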